## 3.4 Outcome

The outcome of interest will be laboratory-confirmed influenza.

# 3.5 Cases

## ILI definition

A case of influenza like illness (ILI) will be defined as an individual who consults a participating GP, presenting a sudden onset of symptoms AND at least one of the following four systemic symptoms:

- fever or feverishness;
- malaise;

- headache;
- myalgia;

AND at least one of the following three respiratory symptoms:

- cough;
- sore throat; and
- shortness of breath.

#### Influenza case

An influenza case will be defined as an ILI case with a respiratory sample positive for influenza.

A pandemic influenza case will be defined as an ILI case with a respiratory sample positive for A(H1N1)v.

**b** Indicators to define cases will be specified in the study annexes.

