#### Laboratory confirmation

Specimens will be collected from ILI cases who consult their GP within seven days of symptom onset.

**b** Mode of specimen collection, storage and transport for each study will be listed in the study annexes.

Influenza laboratory confirmation will be provided by using RT-PCR and/or culture.

**b** RT-PCR characteristics for each study will be listed in the study annexes.

Isolates will undergo a molecular analysis for currently circulating influenza A viruses (subtypes H3 and H1) and (H1N1)v and influenza B. A systematic subset will undergo gene sequencing.

**b** The selection of isolates for each study will be specified in the study annexes.

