# **3.7 Controls**

Various control groups can be selected depending on the available resources. All studies will include at least control group 1 (ILI influenza negative) as defined below.

- Seasonal vaccine: countries will assess whether other control groups could be used in addition to control group 1 (control group selection depends on feasibility).
- **b** The various control groups selected by each study will be detailed in the study annexes.
- Control group 1, ILI flu negative:
  - ILI cases that tested negative for influenza will be included in control group 1.
- Control group 2, non-ILI GP clients (density case-control design):
  - Controls will be selected among GP clients seen at the GP office and selected concurrently to cases (+/- one week from the date of consultation of the corresponding case). Controls will be selected by simple or systematic random sampling among clients who did not yet develop ILI during the influenza season.

**b** Procedures for selection in each of the studies will be detailed in the study annexes. If feasible, controls should be matched by age group (< 75 years; >= 75 years).

- Control group 3, GP clients (case-cohort design):
  - Controls will be selected randomly from a list of GP patients.
  - **b** Procedures for selection in each of the studies will be detailed in the study annexes.
- Control group 4, community controls (density case-control design):
  - Controls are randomly selected individuals living in the same geographical area (defined by postcode or other geographical/administrative division) as the corresponding case. Control individuals have not suffered from ILI during the current influenza season until the corresponding case became ill.
    - **P** Procedures for selection will be detailed in the study annexes.
    - If feasible, controls should be matched by age group (< 75 years; >= 75 years).
- Control group 5, community controls (case cohort):
  - Controls will be randomly selected individuals living in the same geographical area of the corresponding case.
    - **P** Procedures for selection will be detailed in the study annexes.
    - If feasible, controls may be matched by age group (< 75 years; >= 75 years).
- Control group 6, community controls (screening method):
  - For each of the target age groups, vaccine coverage of cases will be compared with the vaccine coverage of the population in the GP catchment area.

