## 3.13 Analysis

Seasonal vaccine: Analysis will be restricted to the groups in each of the participating countries for which seasonal vaccine is recommended.

Pandemic vaccine: Analysis will be restricted to the groups in each of the participating countries for which the pandemic vaccine is recommended.

Analysis will be carried out first for each individual study. In a second step, a pooled analysis is conducted.

All analyses will be done separately for seasonal and pandemic vaccine.

Analyses will be conducted for:

- all data restricted to cases/controls from which swabs were taken < 4 days since the date of onset of symptoms;
- overall VE and strain-specific VE, sample size permitting; and
- the pooled analysis, separately for studies with different control groups (using an unmatched or a matched analysis as appropriate).

Pandemic vaccine: In addition, analysis is conducted for each specific brand.

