# Annex 5: Generated/recoded variables

#### Table: Generated/recoded variables

Variable name	Туре	Values and coding	Definition
caseflu	Numeric (binary)	0 = No 1 = Yes	Indicates ILI case that is lab- confirmed for influenza.
ili	Numeric (binary)	0 = No 1 = Yes	Variable that corresponds to EU ILI case definition (coded using the symptoms in dataset).
panvaccdelay	Numeric (continuous)	Integer	Number of days between pandemic influenza vaccination date and onset date of symptoms (needs to be modified if 2 doses are required).
panvacc	Numeric (binary)	0 = No 1 = Yes	Coded as yes if >14 days between pandemic vaccination and onset of symptoms (needs to be modified if 2 doses are required).
seasvaccdelay	Numeric (continuous)	Integer	Number of days between seasonal influenza vaccination date and onset date of symptoms.
seasvacc	Numeric (binary)	0 = No 1 = Yes	Coded as yes if >14 days between seasonal vaccination and onset of symptoms.
swabdelay	Numeric (continuous)	Unique integer	Number of days between onset date of symptoms and swab date.
swabless4	Numeric (binary)	0 = No 1 = Yes	1 indicates less than 4 days between symptom onset and swab date. 0 indicates more than 3 days.
anychron	Numeric (categorical)	0 = No 1 = Yes 8 = Don't know	0 indicates no chronic disease. 1 indicates at least 1 chronic disease. 8 indicates no chronic disease reported as 'yes' and at least one chronic disease reported as 'unknown'.
smokcurr	Numeric (binary)	0 = No 1 = Yes	Current smoker (1) vs. former smoker or never-smoker (0).
hosp	Numeric (binary)	0 = No 1 = Yes	Not hospitalised for chronic disease in past 12 months (0). Hospitalized for chronic disease in past 12 months (1).
previousflu	Numeric (binary)	0 = No 1 = Yes	Vaccinated with seasonal flu in any of the two years prior to current season.
weekepi	Continuous	Integer	Week of first case coded as 1, subsequent weeks incremental.

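### The primary seasonal VE counts A(H1N1)v infections as seasonal-vaccine failures, because a case is any influenza-positive ILI

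*Protocol*

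**What the plan says.** Section 2.1 makes seasonal VE at age 65 and above a primary objective, next to pandemic VE in the target groups.

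Section 3.4 fixes one outcome for both: "The outcome of interest will be laboratory-confirmed influenza". Section 3.5 adds: "An influenza case will be defined as an ILI case with a respiratory sample positive for influenza". Section 3.6 repeats that influenza-positive ILI cases are influenza cases. Only the pandemic case is tied to a virus: "A pandemic influenza case will be defined as an ILI case with a respiratory sample positive for A(H1N1)v". The seasonal objective has no matching sentence.

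Annex 5 derives one laboratory outcome, caseflu, described as: "Indicates ILI case that is lab- confirmed for influenza". Both example models in Annex 6, two-stage and one-stage, regress caseflu on seasvacc, the seasonal-vaccine indicator.

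Virus-specific results appear elsewhere in a lesser role:
- Section 2.2 lists seasonal VE by subtype as secondary.
- Section 3.13 plans "overall VE and strain-specific VE, sample size permitting" and lists virus strain among the seasonal strata.
- Annex 3 speaks of influenza type-specific VE and, for the pooled strata, virus type.

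The information needed to separate the viruses is planned. Under Laboratory confirmation: "Isolates will undergo a molecular analysis for currently circulating influenza A viruses (subtypes H3 and H1) and (H1N1)v and influenza B". Annex 1 holds lab_virus and lab_subtype.

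**The concern.** The protocol is written for a season in which seasonal strains and A(H1N1)v may circulate together, each with its own vaccine. Section 1 says VE studies may help determine whether seasonal vaccination works against A(H1N1)v, so the protocol does not assume that it does. The primary seasonal estimate nevertheless merges that open question with VE against the strains the vaccine was made for.

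Two things are at stake. First, the estimate would depend on the local virus mix as well as on the vaccine, so it would be hard to compare across countries or across the early, peak and late periods. Second, countries with identical strain-specific VE could show different odds ratios only because their virus mix differs. Annex 3 (Two-stage pooling approach) leaves studies considered heterogeneous out of the two-stage model, so virus mix alone could contribute to excluding a study.

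**Working it through.** **The plan's own figure.** Table 1 gives 89 cases and 89 controls for OR 0.4, coverage 50%, alpha 0.05, power 0.80, one control per case.
- Vaccinated proportion in cases: p1 = OR·c/(1 − c + OR·c) = 0.2/0.7 = 0.2857; in controls p2 = 0.5; d = p2 − p1 = 0.2143.
- Two-proportion formula, two-sided 0.05: n = [1.96·√(2·p̄·(1 − p̄)) + 0.8416·√(p1(1 − p1) + p2(1 − p2))]²/d², with p̄ = 0.3929, gives 80.4.
- Continuity correction: n/4·[1 + √(1 + 4/(n·d))]² = 89.4, which agrees with the stated 89 (90 if rounded up).

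The stated figure is sound. It presumes VE of 60% against whatever is counted as a case.

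**Inputs for the dilution.** OR 0.4 against seasonal strains is the design value in section 3.13. The A(H1N1)v share and the seasonal vaccine's OR against A(H1N1)v are not given, so both are assumed and varied.

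**Formula.** Let f be the A(H1N1)v share of influenza among unvaccinated cases. The controls are the same for both viruses, so the odds ratios average with weights taken from the unvaccinated cases:

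measured OR = (1 − f)·OR(seasonal) + f·OR(A(H1N1)v); measured VE = 1 − OR.

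| f | OR against A(H1N1)v | Measured OR | Measured VE |
|---|---|---|---|
| 0.2 | 1.0 | 0.8·0.4 + 0.2·1.0 = 0.52 | 48% |
| 0.5 | 1.0 | 0.5·0.4 + 0.5·1.0 = 0.70 | 30% |
| 0.8 | 1.0 | 0.2·0.4 + 0.8·1.0 = 0.88 | 12% |
| 0.5 | 0.8 | 0.5·0.4 + 0.5·0.8 = 0.60 | 40% |
| any | 0.4 | 0.40 | 60% |

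The last row marks the limit: with equal protection against both viruses there is no dilution.

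**The same check with the share taken among all cases.** At 50% coverage and OR 1 for A(H1N1)v, the vaccinated proportion in cases is (1 − f)·0.2857 + f·0.5. The required n uses the continuity-corrected formula, rounded up. Power with 90 cases and 90 controls is uncorrected.

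| Share of all cases | Measured VE | n per group | Power with 90/90 |
|---|---|---|---|
| 0 | 60% | 90 | 84% |
| 0.10 | 56% | 111 | 76% |
| 0.25 | 49% | 160 | 59% |
| 0.50 | 35% | 356 | 30% |

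The two tables use different denominators for the share, so their rows do not match one for one; the direction is the same. At coverage 60% and 70%, the 0.50 row gives VE of 37% and 38%.

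**Effect on pooling.** Two countries with the same strain-specific effects (OR 0.4 and 1.0) but f of 0.2 and 0.8 would have true study-level ORs of 0.52 and 0.88. That difference comes from virus circulation alone.

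**Pandemic side.** Section 3.5 limits the pandemic case to A(H1N1)v. Section 3.7 states: "ILI cases that tested negative for influenza will be included in control group 1". An H3 or B positive is therefore neither a pandemic case nor a group 1 control. Annex 5 derives the pandemic exposure (panvacc, panvaccdelay) but no A(H1N1)v outcome to pair with it.

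**The case against.** VE against any laboratory-confirmed influenza is a coherent quantity, and section 1 does not assume that the seasonal vaccine fails against A(H1N1)v. Strain and type strata are planned, typing distinguishes the viruses, the Annex 6 syntax is declared to be guidance only, and section 3.5 delegates detail: "Indicators to define cases will be specified in the study annexes". On this view the viruses will be separated and the only question is which estimate is called primary.

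Part of this stands. Any-influenza VE is worth reporting, and the size of the dilution is unknown and small if little A(H1N1)v circulates in people aged 65 and above. But the strata do not change the primary outcome. Strain-specific VE is conditional on sample size, and the pooled plan in Annex 3 stratifies by type, which read literally keeps H3 and A(H1N1)v together as type A. Leaving the case indicators to country annexes allows countries to settle the matter differently, although a core protocol is meant to fix case definitions and outcome.

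A reader might go further and infer that primary pandemic VE is contaminated too, because caseflu is the only outcome derived in Annex 5. The documents do not support that. Section 3.5 restricts the pandemic case explicitly, both Annex 6 models concern seasvacc only, and Annex 1 carries the virus type and subtype. What remains on that side is a missing derived variable, which would conflict with section 3.5 only if caseflu were reused with panvacc.

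**Conclusion.** The point holds for the primary seasonal VE. As written, A(H1N1)v positives are cases in that analysis, and nothing in the secondary or stratified analyses removes them.

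The direction is toward lower VE if the seasonal vaccine protects less against A(H1N1)v than against seasonal strains. The size rests on two quantities the protocol does not give. With a true VE of 60% and no cross-protection, the estimate is 48% to 12% for A(H1N1)v shares of 20% to 80% in the unvaccinated; with 20% cross-protection and a 50% share it is 40%; with equal protection it stays at 60%. These are illustrations, not forecasts. The added heterogeneity, and any exclusion of studies that follows, is likewise a possibility that depends on how far virus mix differs between countries.

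For pandemic VE the case definition is right, and only the Annex 5 derivation is incomplete.

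**What to change.** 1. In section 3.5, define the primary seasonal case as an ILI case positive for seasonal A(H1), A(H3) or B, identified from lab_virus and lab_subtype. State that A(H1N1)v positives are neither cases nor controls in that analysis.
2. Report seasonal-vaccine VE against A(H1N1)v, and against any influenza, as separate secondary results.
3. In Annex 5, add one seasonal and one A(H1N1)v outcome variable. Use the seasonal one in place of caseflu in the Annex 6 seasvacc models.
4. State how positives without a subtype are handled, since they cannot be assigned to either outcome.

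The change is wording and two recodes, because typing is already planned and recorded. The price is fewer cases in the primary seasonal analysis and the loss of positives that are not subtyped.

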#### Laboratory confirmation

Specimens will be collected from ILI cases who consult their GP within seven days of symptom onset.

**b** Mode of specimen collection, storage and transport for each study will be listed in the study annexes.

Influenza laboratory confirmation will be provided by using RT-PCR and/or culture.

**b** RT-PCR characteristics for each study will be listed in the study annexes.

Isolates will undergo a molecular analysis for currently circulating influenza A viruses (subtypes H3 and H1) and (H1N1)v and influenza B. A systematic subset will undergo gene sequencing.

**b** The selection of isolates for each study will be specified in the study annexes.

## 3.6 Case finding

#### **Case identification**

Cases will be identified among patients that present with ILI to a participating GP.

Following the procedures outlined by each study, all ILI cases (or a systematic sample of them) will be selected and asked to provide a nasal/throat swab specimen for influenza testing. Influenza-positive ILI cases will be considered as influenza cases.

**b** Descriptions of the GPs participating in each of the studies (number, distribution, catchment population) will be available in the study annexes.

**b** Descriptions of procedures on how to select ILI cases for swabbing in each of the targeted groups will be available in the study annexes.

#### Case inclusion criteria

Cases are eligible if they meet the above case definition and accept to participate.

**b** Oral informed consent or written informed consent according to country procedures, as specified in the study annexes.

#### **Case exclusion criteria**

Cases are excluded if they:

- refuse to participate in the study;
- are not eligible for influenza vaccination due to a condition listed in the summary of product characteristics;
- are institutionalised;
- are unable to give informed consent or follow an interview in their native language because of aphasia, reduced consciousness, or other reasons.

Reasons for exclusion will be documented.

# **3.7 Controls**

Various control groups can be selected depending on the available resources. All studies will include at least control group 1 (ILI influenza negative) as defined below.

- Seasonal vaccine: countries will assess whether other control groups could be used in addition to control group 1 (control group selection depends on feasibility).
- **b** The various control groups selected by each study will be detailed in the study annexes.
- Control group 1, ILI flu negative:
  - ILI cases that tested negative for influenza will be included in control group 1.
- Control group 2, non-ILI GP clients (density case-control design):
  - Controls will be selected among GP clients seen at the GP office and selected concurrently to cases (+/- one week from the date of consultation of the corresponding case). Controls will be selected by simple or systematic random sampling among clients who did not yet develop ILI during the influenza season.

**b** Procedures for selection in each of the studies will be detailed in the study annexes. If feasible, controls should be matched by age group (< 75 years; >= 75 years).

- Control group 3, GP clients (case-cohort design):
  - Controls will be selected randomly from a list of GP patients.
  - **b** Procedures for selection in each of the studies will be detailed in the study annexes.
- Control group 4, community controls (density case-control design):
  - Controls are randomly selected individuals living in the same geographical area (defined by postcode or other geographical/administrative division) as the corresponding case. Control individuals have not suffered from ILI during the current influenza season until the corresponding case became ill.
    - **P** Procedures for selection will be detailed in the study annexes.
    - If feasible, controls should be matched by age group (< 75 years; >= 75 years).
- Control group 5, community controls (case cohort):
  - Controls will be randomly selected individuals living in the same geographical area of the corresponding case.
    - **P** Procedures for selection will be detailed in the study annexes.
    - If feasible, controls may be matched by age group (< 75 years; >= 75 years).
- Control group 6, community controls (screening method):
  - For each of the target age groups, vaccine coverage of cases will be compared with the vaccine coverage of the population in the GP catchment area.
    - **P** Procedures for estimating VC will be detailed in the study annexes.

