#### Measure of effect

Vaccine effectiveness will be computed as VE = 1 - OR. An exact 95 % confidence interval will be computed around the point estimate. (For studies using the screening method, refer to the ECDC generic screening protocol.)

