vacc_07	Numeric (categorical)	0 = No 1 = Yes 8 = Do not know	Previous seasonal influenza vaccination 2007-08
anemia_spleen	Numeric (categorical)	0 = No 1 = Yes 8 = Do not know	Enlarged spleen, anaemia
cirrhosis	Numeric (categorical)	0 = No 1 = Yes 8 = Do not know	Cirrhosis
diabetes	Numeric (categorical)	0 = No	Diabetes and endocrine
		1 = Yes 8 = Do not know	
heart_dis	Numeric (categorical)	0 = No 1 = Yes 8 = Do not know	Heart disease
hema_cancer	Numeric (categorical)	0 = No 1 = Yes 8 = Do not know	Hematologic cancer
immuno	Numeric (categorical)	0 = No 1 = Yes 8 = Do not know	Immunodeficiency and organ transplant
lungdis	Numeric (categorical)	0 = No 1 = Yes 8 = Do not know	Lung disease
nonhem_cancer	Numeric (categorical)	0 = No 1 = Yes 8 = Do not know	Nonhematologic cancer
pregn	Numeric (categorical)	0 = No 1 = Yes 8 = Do not know	Pregnancy
ren_disease	Numeric (categorical)	0 = No 1 = Yes 8 = Do not know	Renal disease
dem_stroke	Numeric (categorical)	0 = No 1 = Yes 8 = Do not know	Dementia, stroke
rheumat	Numeric (categorical)	0 = No 1 = Yes 8 = Do not know	Rheumatologic diseases
severity	Numeric (count)	integer	Number of hospitalisations previous year for the chronic disease
gpvisit	Numeric (count)	integer	Number of GP consultations previous year
fs_bath	Numeric (categorical)	0 = No 1 = Yes 8 = Do not know	Requires assistance to bathe

Variable name	Туре	Values and coding	Definition
fs_walk	Numeric (categorical)	0 = No 1 = Yes 8 = Do not know	Requires assistance to walk
smoking		0 = Never 1 = Former 2 = Current 9 = Do not know	Never, former (stopped smoking at least 1 year before inclusion in the study), current smoker
antivir	Numeric (categorical)	0 = No 1 = Yes 8 = Do not know	Administration of antivirals
antivirdate	Date	dd/mm/yyyy	Date administration antiviral
antivirtype	Text		Type of antiviral (brand name)
prev_h1n1	Numeric (categorical)	0 = No 1 = Yes 8 = Do not know	Lab-confirmed A(H1N1)v prior to study.
res_home	Numeric (categorical)	0 = No 1 = Yes 8 = Do not know	Exclusion criteria: living in a residential home
contra	Numeric (categorical)	0 = No 1 = Yes 8 = Do not know	Exclusion criteria: contraindication for influenza vaccination
dens_cc	Numeric (categorical)	0 = No 1 = Yes	Exclusion criteria for density case- control: ILI symptoms in the season

This table represents a selection of confounders. Variables can be included or excluded as necessary.

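### In the optional density comparisons (control groups 2 and 4), an earlier ILI in the season rules out controls but not cases, so VE from these comparisons can be biased in either direction

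*Protocol*

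**What the plan says.** Section 3.7 describes two control groups as density case-control designs.

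- Group 2 (GP clients): "Controls will be selected by simple or systematic random sampling among clients who did not yet develop ILI during the influenza season".
- Group 4 (community): "Control individuals have not suffered from ILI during the current influenza season until the corresponding case became ill".

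Both rules concern ILI of any cause. The endpoint is narrower. Section 3.4 states: "The outcome of interest will be laboratory-confirmed influenza". Section 3.5 adds: "An influenza case will be defined as an ILI case with a respiratory sample positive for influenza".

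On the case side, section 3.6 says: "Cases are eligible if they meet the above case definition and accept to participate". Its exclusion list covers refusal, ineligibility for vaccination, institutionalisation and inability to consent or be interviewed. It does not mention an earlier ILI.

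Annex 1 has a variable, dens_cc, described as an exclusion criterion for the density design: "ILI symptoms in the season". It is coded no/yes and has no date. The Annex does not say whether it applies to cases, controls or both.

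On reach, section 3.7 says: "All studies will include at least control group 1 (ILI influenza negative) as defined below". Other control groups depend on feasibility. Groups 1, 3 and 5 carry no earlier-ILI restriction.

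**The concern.** Density sampling works because controls represent the people who, at the time a case arises, could still become a case. Someone who had an influenza-negative ILI earlier in the season is still at risk of laboratory-confirmed influenza and counts as a case if later positive. The rules for groups 2 and 4 remove that person from the pool of controls but not from the pool of future cases, so the two sides come from different populations.

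The consequence runs through vaccine coverage in the controls. The Protocol itself gives reasons why earlier ILI could go with vaccination in either direction. Section 3.15 expects high-risk people to be vaccinated more often, and also describes a healthy-vaccinee pattern. If vaccinated people have more earlier ILI, the rule lowers control coverage and VE is understated. If they have less, VE is overstated. Earlier ILI can only accumulate as the season goes on, so any such bias would be larger in late strata than in early ones.

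**Working it through.** **Plan's own figure.** The Protocol gives no figure for earlier ILI. The base case here is its planning example: 50% coverage and OR 0.4, that is VE 60% (section 3.13, Tables 1 and 2). The 89 cases and 89 controls stated there at 80% power are reproduced to within one by the two-proportion formula with continuity correction (90; 81 without the correction). No sample size is in dispute.

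**Formula.** Effect measure (section 3.13): "Vaccine effectiveness will be computed as VE = 1 - OR". Let V and U be the vaccinated and unvaccinated shares of people still free of influenza, and let pV and pU be the proportions of each with an earlier non-influenza ILI.

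- Vaccination odds in cases, if earlier ILI does not change influenza risk: OR_true × V/U.
- Vaccination odds in controls restricted to no earlier ILI: V(1−pV) / [U(1−pU)].
- Hence OR_obs = OR_true × (1−pU)/(1−pV). Coverage cancels.

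**Results for true OR 0.40.** All p values are assumptions.

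| pU | ratio pV/pU | pV | (1−pU)/(1−pV) | OR_obs | VE |
|---|---|---|---|---|---|
| any | 1.0 | = pU | 1.000 | 0.400 | 60.0% |
| 5% | 0.8 | 4% | 0.95/0.96 = 0.990 | 0.396 | 60.4% |
| 5% | 1.5 | 7.5% | 0.95/0.925 = 1.027 | 0.411 | 58.9% |
| 10% | 0.8 | 8% | 0.90/0.92 = 0.978 | 0.391 | 60.9% |
| 10% | 1.2 | 12% | 0.90/0.88 = 1.023 | 0.409 | 59.1% |
| 10% | 1.5 | 15% | 0.90/0.85 = 1.059 | 0.424 | 57.6% |
| 20% | 2.0 | 40% | 0.80/0.60 = 1.333 | 0.533 | 46.7% |

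The 5 to 10% rows with ratios other than 1 give shifts of about 0.4 to 2.4 points. The last row shows that a large shift needs frequent earlier ILI together with a strong link to vaccination.

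**If earlier ILI also marks a doubled influenza risk** (pU 10%, pV 15%):

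- Case odds ratio against the full risk set: 0.4 × (0.85 + 2×0.15)/(0.90 + 2×0.10) = 0.4 × 1.15/1.10 = 0.418. Density controls with no ILI restriction would give VE 58.2%.
- Rule as written: 0.418 × 0.90/0.85 = 0.443, VE 55.7%.
- Same earlier-ILI exclusion for cases and controls: 0.4 × [(1−pV)/(1−pU)] / [(1−pV)/(1−pU)] = 0.40, VE 60%.

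The symmetric rule restores 60% in every scenario.

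**Precision for comparison.** With 90 cases and 90 controls, control coverage is 50% and case coverage is 0.5×0.4/(1 − 0.5×0.6) = 28.6%. The SE of log OR is √(1/45 + 1/45 + 1/25.7 + 1/64.3) ≈ 0.31, and the 95% CI for VE is about 26% to 78%.

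**The case against.** The strongest objection is to the step from asymmetry to bias, and it stands. A reader might infer that VE from groups 2 and 4 is biased as a matter of course. The formula does not support that: with equal earlier-ILI frequency in vaccinated and unvaccinated people, VE stays at 60% whatever the frequency. The Protocol gives neither the frequency nor the association.

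Size is also limited. Section 3.5 defines an ILI case as someone who consults a participating GP. If the control rule is read that way, p is the share with an earlier medically attended ILI, which may be small; 2% against 3% gives 0.4 × 0.98/0.97 = 0.404, VE 59.6%. The figures above are crude. The example models in Annex 6 adjust for chronic disease, functional status, hospital admission, GP visits and week, which should remove part of any association. They cannot remove all of it by adjusting for earlier ILI itself, because no density control has one.

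A reader might also infer that the mismatch would imitate a change in VE between early, peak and late season. The direction of growth is right, but a drift of about 2 points would not be visible against an interval of roughly 26% to 78% in a stratum of 90 and 90.

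Reach is narrow too. Groups 2 and 4 are optional, and section 3.13 runs the pooled analysis separately by control group, so the group 1 estimate is not contaminated.

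Two defences of the text hold only in part. First, dens_cc may have been meant for both sides, as the neighbouring exclusion items for residential home and contraindication are. But every case has ILI symptoms in the season, so the item as worded would exclude every case. It needs the notion of an earlier episode and a date. Second, excluding any earlier ILI is a workable stand-in for earlier influenza when density controls are not described as swabbed. That justifies the rule for controls; it does not explain why cases are exempt.

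**Conclusion.** The mismatch is in the text: in the group 2 and 4 comparisons, people with an earlier non-influenza ILI can be cases but not controls, and dens_cc as written does not resolve this. VE from these comparisons can be biased in either direction if earlier ILI is associated with vaccination after adjustment. On assumed inputs of 5 to 10% earlier ILI in unvaccinated people and a ratio of 0.8 to 1.5, with no effect of earlier ILI on influenza risk, a true VE of 60% shifts by about 0.4 to 2.4 points before adjustment; at a ratio of 1 it does not shift. The documents do not support a claim of definite bias, of a fixed direction, or of any effect of this rule on the mandatory group 1 or on groups 3 and 5. Severity is minor: a cheap improvement to a core text on which the country annexes build.

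**What to change.** In sections 3.6 and 3.7 and in Annex 1:

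- State that, for comparisons with control groups 2 and 4, the exclusion for an earlier ILI in the season applies to cases as well as controls.
- Redefine dens_cc as an ILI episode before the onset of the current case episode, or before the control's reference date. Record its date and ask it of cases too.
- Keep all cases in the comparison with control group 1.

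The cost is one extra dated question for cases and a small loss of cases from the group 2 and 4 comparisons. Limiting the control exclusion to earlier influenza is an alternative, but it needs a test result that density controls may not have, and it leaves some bias if earlier ILI marks a higher influenza risk (58.2% rather than 60% in the example above).
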